**Table 5.9-3 GA101 administration during ASCT – Safety set**

	Safety set N=XX
Total dose taken (mg/m^2)	
N	XX
Missing	XX
Mean (SD)	XX.X (XX.XX)
Median	XX.X
Q1 ; Q3	XX ; XX
Min ; Max	XX ; XX
PPD (%)	
N	XX
Missing	XX
Mean (SD)	XX.X (XX.XX)
Median	XX.X
Q1 ; Q3	XX ; XX
Min ; Max	XX ; XX
PPD (%)	
< 75%	XX (XX.X%)
[75% - 90%]	XX (XX.X%)
[90% - 110%]	XX (XX.X%)
[110% - 125%]	XX (XX.X%)
>= 125%	XX (XX.X%)

Expected total dose during asct for GA101 : 1000mg.

Total dose is the sum of dose administered during asct.

PPD = (Total dose taken/total dose expected)/100

**Table 5.9-4 GA101 administration during maintenance – Safety set**

	Safety set N=XX
Total dose taken (mg/m^2)	
N	XX
Missing	XX
Mean (SD)	XX.X (XX.XX)
Median	XX.X
Q1 ; Q3	XX ; XX
Min ; Max	XX ; XX
PPD (%)	
N	XX
Missing	XX
Mean (SD)	XX.X (XX.XX)
Median	XX.X
Q1 ; Q3	XX ; XX
Min ; Max	XX ; XX
PPD (%)	
< 75%	XX (XX.X%)
[75% - 90%]	XX (XX.X%)
[90% - 110%]	XX (XX.X%)
[110% - 125%]	XX (XX.X%)
>= 125%	XX (XX.X%)

Expected total dose during maintenance for GA101 : 1000mg every 2 months.

Total dose is the sum of dose administered during maintenance.

PPD = (Total dose taken/total dose expected)/100

**Table 5.9-5 GA101 administration during maintenance on-demand – Safety set**

		Safety set N=XX
Total dose taken (mg/m^2)		
N		XX
Missing		XX
Mean (SD)		XX.X (XX.XX)
Median		XX.X
Q1 ; Q3		XX ; XX
Min ; Max		XX ; XX
PPD (%)		
N		XX
Missing		XX
Mean (SD)		XX.X (XX.XX)
Median		XX.X
Q1 ; Q3		XX ; XX
Min ; Max		XX ; XX
PPD (%)		
< 75%		XX (XX.X%)
[75% - 90%]		XX (XX.X%)
[90% - 110%]		XX (XX.X%)
[110% - 125%]		XX (XX.X%)
>= 125%		XX (XX.X%)

Expected total dose during maintenance for GA101 if positive MRD : 3000mg for the 1st month and then 1000mg every month.

Total dose is the sum of dose administered during maintenance on-demand.

PPD = (Total dose taken/total dose expected)/100

**Table 5.9-6 Patients with at least one dose interruption of GA101 – Safety set**

		Safety set N=XX
Patients with at least one dose interruption of GA101		
No		XX (XX.X%)
Yes		XX (XX.X%)

**Listing 5.9-1 Patients with at least one dose interruption of GA101 – Safety set (XX patients)**

Patient identification number	Inclusion date	Number of cycles received	Adverse Event					
			Period	Description	Highest grade	Relationship with GA101	Action taken on GA101	Outcome
XXXXX	XX/XX/XXXX	XX	XX	XX	X	XX	XX	XX

Filter: Action taken on GA101 = Drug interrupted

## 5.10 Safety analysis

### 5.10.1 Adverse Events

**Table 5.101-1 Summary of AEs – Safety set**

	Induction N=XX	ASCT N=XX	Maintenance N=XX	Total N=XX
Patients with at least one AE				
No	XX (XX.X%)	XX (XX.X%)	XX (XX.X%)	XX (XX.X%)
Yes	XX (XX.X%)	XX (XX.X%)	XX (XX.X%)	XX (XX.X%)
If yes, number of Aes by patients				
N	XX	XX	XX	XX
Missing	XX	XX	XX	XX
Mean (SD)	XX.X (XX.XX)	XX.X (XX.XX)	XX.X (XX.XX)	XX.X (XX.XX)
Median	XX.X	XX.X	XX.X	XX.X
Q1 ; Q3	XX ; XX	XX ; XX	XX ; XX	XX ; XX
Min ; Max	XX ; XX	XX ; XX	XX ; XX	XX ; XX
Patient with at least one AE of grade >= 3				
No	XX (XX.X%)	XX (XX.X%)	XX (XX.X%)	XX (XX.X%)
Yes	XX (XX.X%)	XX (XX.X%)	XX (XX.X%)	XX (XX.X%)
Patient with at least one fatal AE				
No	XX (XX.X%)	XX (XX.X%)	XX (XX.X%)	XX (XX.X%)
Yes	XX (XX.X%)	XX (XX.X%)	XX (XX.X%)	XX (XX.X%)
Patient with at least one AE leading to treatment discontinuation				
No	XX (XX.X%)	XX (XX.X%)	XX (XX.X%)	XX (XX.X%)
Yes	XX (XX.X%)	XX (XX.X%)	XX (XX.X%)	XX (XX.X%)
Patient with at least one AESI*				
No	XX (XX.X%)	XX (XX.X%)	XX (XX.X%)	XX (XX.X%)
Yes	XX (XX.X%)	XX (XX.X%)	XX (XX.X%)	XX (XX.X%)

\* AESI = Tumor Lysis Syndrom and IRR grade 4 occuring during or within 24 hours after the GA101 infusion.

**Table 5.101-2 Summary of related AEs – Safety set**

	Induction N=XX	ASCT N=XX	Maintenance N=XX	Total N=XX
Patients with at least one related AE				
No	XX (XX.X%)	XX (XX.X%)	XX (XX.X%)	XX (XX.X%)
Yes	XX (XX.X%)	XX (XX.X%)	XX (XX.X%)	XX (XX.X%)
If yes, number of related Aes by patients				
N	XX	XX	XX	XX
Missing	XX	XX	XX	XX
Mean (SD)	XX.X (XX.XX)	XX.X (XX.XX)	XX.X (XX.XX)	XX.X (XX.XX)
Median	XX.X	XX.X	XX.X	XX.X
Q1 ; Q3	XX ; XX	XX ; XX	XX ; XX	XX ; XX
Min ; Max	XX ; XX	XX ; XX	XX ; XX	XX ; XX
Patient with at least one related AE of grade >= 3				
No	XX (XX.X%)	XX (XX.X%)	XX (XX.X%)	XX (XX.X%)
Yes	XX (XX.X%)	XX (XX.X%)	XX (XX.X%)	XX (XX.X%)
Patient with at least one fatal related AE				
No	XX (XX.X%)	XX (XX.X%)	XX (XX.X%)	XX (XX.X%)
Yes	XX (XX.X%)	XX (XX.X%)	XX (XX.X%)	XX (XX.X%)
Patient with at least one related AE leading to treatment discontinuation				
No	XX (XX.X%)	XX (XX.X%)	XX (XX.X%)	XX (XX.X%)
Yes	XX (XX.X%)	XX (XX.X%)	XX (XX.X%)	XX (XX.X%)
Patient with at least one related AESI*				
No	XX (XX.X%)	XX (XX.X%)	XX (XX.X%)	XX (XX.X%)
Yes	XX (XX.X%)	XX (XX.X%)	XX (XX.X%)	XX (XX.X%)

\* AESI = Tumor Lysis Syndrom and IRR grade 4 occuring during or within 24 hours after the GA101 infusion.

**Table 5.101-3 AEs by SOC and PT – Safety set**

	Safety set N=XX
AEs	XX (XX.X%)
SOC 1	XX (XX.X%)
PT 1	XX (XX.X%)
PT ...	XX (XX.X%)
SOC ...	XX (XX.X%)
PT 1	XX (XX.X%)
PT ...	XX (XX.X%)

**Table 5.101-4 Description of AEs by SOC/PT and by highest intensity – Safety set**

System Organ Class	Grade 3 N=XX		Grade 4 N=XX		Grade 5 N=XX	
	Patients	Events	Patients	Events	Patients	Events
AEs	XX (XX.X%)					
SOC 1	XX (XX.X%)					
PT 1	XX (XX.X%)					
PT ...	XX (XX.X%)					
SOC ...	XX (XX.X%)					
PT 1	XX (XX.X%)					
PT ...	XX (XX.X%)					

**Table 5.101-5 Characteristics of AEs – Safety set**

	Safety set N=XX
Onset period	
Before pr-phase	XX (XX.X%)
Pre-phase	XX (XX.X%)
Induction	XX (XX.X%)
ASCT	XX (XX.X%)
Maintenance	XX (XX.X%)
Maintenance on-demand	XX (XX.X%)
Follow-up	XX (XX.X%)
Highest intensity	
1	XX (XX.X%)
2	XX (XX.X%)
3	XX (XX.X%)
4	XX (XX.X%)
5	XX (XX.X%)
Relationship with GA101	
Unrelated	XX (XX.X%)
Related	XX (XX.X%)
Not applicable	XX (XX.X%)
Relationship with DHAP	
Unrelated	XX (XX.X%)
Related	XX (XX.X%)
Not applicable	XX (XX.X%)
Relationship with ASCT	
Unrelated	XX (XX.X%)
Related	XX (XX.X%)
Not applicable	XX (XX.X%)
Serious AE	
No	XX (XX.X%)
Yes	XX (XX.X%)
AESI*	
No	XX (XX.X%)
Yes	XX (XX.X%)
Outcome	
Not recovered/Not resolved	XX (XX.X%)
Recovered/Resolved	XX (XX.X%)
Recovered/Resolved with sequelae	XX (XX.X%)
Recovering/Resolving	XX (XX.X%)
Fatal	XX (XX.X%)

\* AESI = Tumor Lysis Syndrom and IRR grade 4 occurring during or within 24 hours after the GA101 infusion.

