Safety consideration	
Time of Analysis
 
Given the fact that primary endpoint is prematurely determined in study treatment period, 2 types of analysis will be performed:
 
 • Primary criterion analysis • Final analysis 
Primary criterion analysis:
 
Primary criterion analysis will be performed once all patients included in efficacy set (70 evaluable patients) have completed 4 cycles of treatment or treatment discontinued prior to cycle 4 of the study and will consist of analyzing:
 
 • Primary criterion : MRD rate in bone marrow after the 4 cycles or at treatment discontinuation of GA-DHAP • Treatment exposure • Stem cell collection failure • Secondary safety endpoints 
Final analysis:
 
All analyses will be performed when all included patients will have performed the end of treatment visit (end of maintenance “on demand” period or treatment discontinued from the study).
 
 • AE of grade 3-5 (CTCAE – v 4.03) regardless the relationship to IMP occurring from the date of informed consent signature, and up to 28 days after last treatment administration, will be recorded on the AE pages of eCRF. • Some adverse events which are attributable to the ASCT procedure only and not to the study drug are not to be entered in the eCRF (listed in section 14.2). • Any grade for AESI will be collected from ICF signature and until 28 days after last treatment administration regardless the relationship to IMP • All events that meet one or more criteria of seriousness, regardless the relationship to IMP, occurring from the date of the informed consent signature, during treatment administration period and up to 28 days after last drug administration, will be reported as SAE.

	
A SAE that occurs after this time, including follow up period, will be reported if considered related to IMP.
 
In a case of SAE the Investigator must immediately (within 24 hours):
 
SEND the SAE pages to LYSARC Pharmacovigilance department: [contact] OR EMAIL TO [contact]
 
Pregnancy and suspected pregnancy will be reported on Pregnancy Form to LYSARC PV from the date of informed consent signature and up to 28 days after the last study drug administration.

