5 BACKGROUND AND STUDY RATIONALE

5.1 Use of DHAP followed by ASCT in front line in MCL

The experts of The EBMT/EMCL consensus for treatment of young untreated patients with MCL concluded that Autologous Stem Cell Transplant (ASCT) is the standard first-line consolidation therapy and that induction therapy should include high-dose cytarabine and Rituximab (Robinson et al. Leukemia. 2015 Feb). The LyMa101 trial follows this recommendation.

A front to front comparison between induction with R-CHOP alone versus alternating R-CHOP/R-DHAP demonstrated the benefice of cytarabine-containing regimen before ASCT (Hermine abstract ASH 2012; Delarue et al. Blood. 2013 Jan). Indeed, the use of cytarabine increases both complete remission rate (CR) and response duration. More recently, the first interim analyses of the LYSA trial for young untreated MCL patients, so-called LyMa, have been presented at the American society of Hematology (ASH) (le Gouill et al, ASH 2012, 2014). The LyMa trial was a phase III international trial that addressed the question of a Rituximab maintenance after ASCT. The induction chemotherapy regimen before ASCT in the LyMa trial consisted of only 4 courses of rituximab, cytarabine plus cisplatin (R-DHAP regimen) instead of 3 courses of R-CHOP plus 3 courses of R-DHAP in the previous trial (Hermine abstract ASH 2012). Interim analyses demonstrate that CR rate including at the molecular level and progression-free survival (PFS) for all patients are similar after 4xR-DHAP than after 6 courses of alternating R-CHOP/R-DHAP. Therefore, the design of the present LyMa101 trial is similar to the previous LyMa trial with 4 courses of DHAP. Rituximab will be replaced by the new generation of anti-CD20 antibody Obinutuzumab (See below).

A debulking by COP could be recommended before administration of chemotherapy for high-risk tumor lysis syndrome patients (Jabbour et al. Rev. Med. 2005; Ribrag et al. The Lancet. 2016 Jun 11). This decision will be led by investigator's judgment.

Regarding conditioning regimen of ASCT, there is no evidence that total body irradiation (TBI) is superior to non-TBI containing chemotherapy conditioning regimen like BEAM (BCNU, Etoposide, cytarabine, melphalan) (Touzeau et al. Ann Hematol. 2014 Feb). BEAM is easier to use in clinical practice than TBI and risk of myelodysplasia is lower. Therefore, BEAM is the more frequently used conditioning regimen in MCL.

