14.2 Adverse Events reporting rules

Due to expected toxicity of study treatment, all AEs of grade 3-5 for toxicities (hematological or non-hematological) (CTCAE – version 4.0) regardless relationship to investigational product occurring from the date of informed consent signature to 28 days after the last study drug administration of the study will be recorded in the AE pages of the eCRF. When associated to a SAE and regardless the time of occurrence and the grade, the AE must be reported as "Adverse Event" in the appropriate eCRF pages.

Whenever possible, symptoms should be grouped as a single syndrome or diagnosis. The investigator should specify the date of onset, intensity, action taken regarding trial medication, corrective therapy given, outcome of all AEs and his opinion as to whether the AE can be related to the study drugs.

All events that meet one or more criteria of seriousness (see Section 13.1.2.) will be reported as SAE (see Section 13.3).

General AE reporting rules:

- Non-serious AE will be reported through eCRF
- Any episode of any grade of toxicity, related to a SAE must be reported as "Adverse Event" in the appropriate eCRF pages regardless the time of occurrence
- Signs, symptoms and physical findings indicative of lymphoma or progression of lymphoma are not to be reported as "Adverse Event"
- "Alopecia" toxicity (any grade) will never be reported as "Adverse event"
- AEs will be considered ended (recovered without sequelae) when recovered to a grade 0 or baseline
- In case of screening failure, at least AEs corresponding to SAEs will be reported in the AEs pages of eCRF.
- When a medical history resolves or decreases at a grade lower than baseline, the new grade will be the new reference grade for following AEs
- For laboratory abnormalities, the laboratory test to be taken as reference will be the one performed nearest to the Cycle 1 Day 1.

Abnormal laboratory values reporting rules:

If a laboratory abnormality is one component of a diagnosis or syndrome (e.g., alkaline phosphatase and bilirubin 5 × ULN associated with cholecystitis), only the diagnosis (e.g., cholecystitis) or syndrome should be recorded on the AE page/screen of the eCRF. If the laboratory abnormality was not a part of diagnosis or syndrome, the laboratory abnormality should be recorded as an AE.

An abnormal laboratory value which is not a component of a diagnosis or syndrome is considered as an AE if the abnormality:

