14.3 Serious Adverse Events reporting rules

All events that meet one or more criteria of seriousness (see Section 13.1.2.) will be reported **continuously** from the date of informed consent signature to 28 days after the last study drug administration of the maintenance period. During maintenance on-demand, if GA101 is discontinued (temporarily or permanently), SAEs will be reported until 28 days after last study drug administration. If GA101 is reintroduced (according to MRD results), SAEs will further be reported according to the same reporting rules.

SAE will be reported regardless:

- the relationship to the study treatment
- the administration of new lymphoma therapy,
- disease progression.

Nevertheless, the following SAEs that occur during maintenance on-demand beyond 28 days after the last administration of GA101 will be reported as SAEs regardless relationship to study treatment:

- Death
- Life-threatening events
- Severe infections, hepatitis, progressive multi-focal encephalopathy
- Cardiac events
- Neutropenia

To note that all SAEs **considered related to the study medication** will **always** be reported even if occur beyond 28 days after the last administration of GA101 including during the follow-up period.

Whenever possible, symptoms should be grouped as a single syndrome or diagnosis. The investigator should specify the date of onset, intensity, action taken regarding the study medication, corrective therapy given, outcome of all SAEs and his/her opinion as to whether the SAE can be related to the IMP.

General SAE reporting rules:

- Any episode of any grade of toxicities, which meets one of the seriousness criteria must be reported as "Serious Adverse Event" in the appropriate SAE form
- Signs, symptoms and physical findings indicative of lymphoma or progression of lymphoma are not to be reported as "Serious Adverse Event"
- Hospitalizations **not to be considered** as SAE are:
 - Planned hospital admissions or surgical procedures for an illness or disease which existed before the patient was enrolled in the study or before the study drug was given are not to be considered SAEs unless the condition deteriorated in an unexpected manner during the study (eg surgery was performed earlier than planned).
 - A procedure for protocol therapy administration or protocol/disease-related investigations. Hospitalization or prolonged hospitalization for a complication will be reported as an SAE

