### 4.4.4 Safety Set (SS)

The Safety set will include all patients having signed the informed consent and received at least one dose of the IMP study drug (Obinutuzumab).

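### The SAP defines no treatment-emergent window, so all-cause AE, SAE and AESI totals mix on-drug events with pre-dose and drug-free on-demand events, and most tables cannot separate them

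*SAP*

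**What the plan says.** **Collection.** Protocol 14.2 records grade 3-5 AEs "occurring from the date of informed consent signature to 28 days after the last study drug administration of the study". For AESIs the synopsis states: "Any grade for AESI will be collected from ICF signature and until 28 days after last treatment administration regardless the relationship to IMP". For SAEs, Protocol 14.3 has a rule for the on-demand phase: "During maintenance on-demand, if GA101 is discontinued (temporarily or permanently), SAEs will be reported until 28 days after last study drug administration". Reporting resumes if the drug is reintroduced. Five listed kinds of SAE, and every related SAE, are still reported beyond that limit.

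**Pre-phase.** Protocol 5.1 says "A debulking by COP could be recommended before administration of chemotherapy for high-risk tumor lysis syndrome patients". Under Protocol 10.2, COP starts after inclusion, and cycle 1 begins one week after COP ends.

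**AESI definition.** Protocol 14.5 lists TLS with no timing condition, and grade 4 infusion-related reactions (IRR) during or within 24 hours after an infusion. The SAP footnote puts both into one phrase, so it is unclear whether the 24-hour clause also covers TLS.

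**Analysis.** All AE, SAE and AESI tables in SAP 5.10.1 and 5.10.2 use the Safety set, meaning patients with at least one obinutuzumab dose. SAP 3.2.3 requires AEs and SAEs to be described by SOC and PT for each period. Table 5.101-5 lists onset periods starting with "Before pr-phase" and pre-phase and including on-demand maintenance. Table 5.102-4 does much the same for SAEs, starting at pre-phase.

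**The concern.** Tolerability of obinutuzumab at induction and on demand is a stated secondary objective (Protocol 6.2, SAP 3.1.2). A reader of the safety tables will want the event rate while patients were exposed. Two kinds of unexposed time fall within collection.

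The first runs from consent to the first obinutuzumab dose. In some patients it includes COP, a cytoreductive pre-phase aimed at those at high risk of tumour lysis. TLS is one of only two AESIs, so a small number of COP-related events could dominate that line.

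The second is on-demand maintenance, in which MRD-negative patients receive no drug (Protocol 10.2.3). A single on-demand figure would mix treated and untreated time. For non-serious AEs, whether an event in a gap is collected at all depends on what happens to the patient later.

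**Working it through.** The plan gives no figure on this point to reproduce. The check sets the collection rules against the table layouts and then illustrates the size.

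**1. Do pre-dose events enter?** Collection opens at consent (Protocol 14.2; synopsis for AESIs). COP starts after inclusion and runs D1 to D5, with cycle 1 a week later, so about 5 + 7 = 12 days on study precede the first obinutuzumab dose. The Safety set restricts patients, not dates. Anyone who goes on to receive obinutuzumab therefore brings pre-dose events into the tables. Under Protocol 14.5, TLS in those days is an AESI.

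**2. Do drug-free on-demand events enter?**
- *SAEs:* the kinds listed in 14.3 and all related SAEs are reported beyond 28 days off drug. Under 14.2, an AE associated with an SAE is recorded whatever its timing, so these reach the AE tables as well.
- *Non-serious grade 3-5 AEs:* the 14.2 window ends 28 days after the last administration of the study. An event more than 28 days into a gap is inside the window only if the patient is later re-treated, which is unknown when the event occurs.

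**3. Can the tables separate them?**

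| SAP output | Period shown | What is missing |
|---|---|---|
| Tables 5.101-1, 5.101-2 (AE and related-AE summaries, including AESI) | Induction, ASCT, Maintenance, Total | No pre-phase or on-demand column; the SAP does not say where such events go |
| Tables 5.101-3, 5.101-4 (SOC/PT; SOC/PT by grade) | None | The by-period split required by SAP 3.2.3 |
| Table 5.102-2 and the two SOC/PT tables numbered 5.102-3 (SAEs) | None | Any period split; for the SOC/PT tables, the one required by 3.2.3 |
| Tables 5.101-5, 5.102-4 (characteristics) | Onset period as its own set of rows | AESI and grade not crossed with period; on-demand not split by exposure; relationship to GA101, DHAP and ASCT but not COP |
| Listings of fatal AEs, AEs leading to discontinuation, AESIs and SAEs | Onset date and event period for each event | Patient-level only; no rates |

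**4. Size, pre-dose side.** Neither COP use nor TLS incidence is documented. Assume a Safety set between 70 (the evaluable target) and 83 (planned enrolment). Each patient whose only AESI is a pre-dose TLS adds 1/N:
- one patient: 1/83 = 1.2% to 1/70 = 1.4%;
- three patients: 3/83 = 3.6% to 3/70 = 4.3%.

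**5. Size, on-demand side.** Three years are 3 × 365.25 = 1,095.75 days. Suppose a patient has one re-treatment course of m months (assumed; 30.44 days each) plus a 28-day tail. The off-drug share is 1 − (30.44m + 28)/1,095.75:
- m = 3: 1 − 119.32/1,095.75 = 89%;
- m = 24: 1 − 758.56/1,095.75 = 31%.

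The tail of the last scheduled maintenance dose could lower these by up to 28/1,095.75 = 2.6 points. They are also upper bounds on gap time inside the 14.2 window, because only the part before the last course counts. They show why one on-demand column is not an on-drug rate.

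**The case against.** The strongest reply is that the tables never claim to be drug-attributed. A reader might infer that pre-dose and off-drug events are being charged to obinutuzumab. The documents do not support that. The counts are all-cause, both characteristics tables report relationship to GA101 as unrelated, related or not applicable, and there are separate related-AE and related-SAE tables. The row "Before pr-phase" is itself a device for setting pre-dose events apart, and the AESI listing would show a TLS during COP with its date and period. All of this stands. It leaves the totals, SOC/PT, grade and AESI rates without a matching split.

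A reader might also infer that events from a full three-year drug-free period enter the AE window. For non-serious AEs they do not. A patient who is never re-treated leaves the window 28 days after the last maintenance dose, and afterwards only events reportable under 14.3 are collected.

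Third, a strict on-drug window applied to every SAE table would remove late and related SAEs that 14.3 deliberately collects. That is correct, and it is why the flag should supplement the all-cause tables and not replace them.

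Fourth, if the 24-hour clause in the SAP footnote is read as covering TLS, a COP-related TLS would not count as an AESI. The wording allows that reading, but Protocol 14.5 attaches the clause to IRR alone.

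**Conclusion.** The point holds as a gap in the SAP's safety analysis. With no treatment-emergent definition, the all-cause AE, SAE and AESI totals combine on-drug events with pre-dose events and with some drug-free on-demand events. The existing rows and listings undo this only in part. The missing period split in the SOC/PT tables also departs from SAP 3.2.3.

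The numerical effect cannot be fixed from the documents. The 1.2 to 1.4 points per patient rests on an assumed Safety set of 83 to 70, and the number of such patients is unknown and may be zero. For on-demand tolerability the problem is more structural: the only on-demand display in the AE and SAE summary tables is one onset row that pools exposed and unexposed time, and non-serious AEs in gaps are captured according to later re-treatment.

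None of this touches the primary MRD analysis. It bears on a stated secondary objective and should be corrected before the final safety tables are produced.

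**What to change.** Change SAP 3.2.3 and 5.10 only:

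- Derive a treatment-emergent flag: onset or worsening from the first obinutuzumab dose to 28 days after the last dose of each course, re-entering the window on re-treatment.
- Present the AE, SAE, AESI and SOC/PT tables by period, with pre-phase and on-demand columns, and split on-demand into on-drug and off-drug. This also supplies the split that 3.2.3 already requires.
- Show events before the first obinutuzumab dose separately.
- State in the AESI footnote that the 24-hour clause applies only to IRR, as in Protocol 14.5.
- Keep the all-cause totals, and keep the late or related SAEs collected under 14.3, alongside the flagged tables.
- Note under the off-drug on-demand column that non-serious AEs there are incompletely ascertained, because of the 14.2 window.

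The cost is one derived flag and a few more columns, using onset and dosing dates already collected. Changing collection under Protocol 14.2 is not proposed. It would need an amendment with ethics and authority approval (Protocol 18.9). With SAP version 2.0 effective in October 2024 and the last visit planned for the first quarter of 2025, it would come too late to help.
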